**Table 8-2 Assessment schedule for Cohort 1 (Moderna vaccine)**

Period	Screening	Treatment									Follow-up	
		Visit 1 Screening	Visit 2 (home visit)	Visit 3 (home visit)	Visit 4 (office visit)	Visit 5 Visit 6 Visit 7 (home visit)	Visit 8 (office visit)	Visit 9 (office visit)	Visit 10 (office visit)	Visit 11/ End of Study – EOS (office visit)		
Visit Name												
Day/Week/Month	Day -7	Day 1	Day 29	Day 43	Day 50 Day 57 Day 71	Day 99	Day 209	Day 299	Day 389	Day 419		
Visit Window					+/-3d	+/-3d	+/-3d	+/-3d	+/-3d	+/-3d		
Obtain informed consent	X											
Inclusion/exclusion criteria	X											
Demography	X											
Relevant medical history/current medical history	X											
Non-drug therapies and procedures	X	X	X	X	X	X	X	X	X	S	X	
Prior/Concomitant Medications	X	X	X	X	X	X	X	X	X	S	X	
MS Relapse	X	X	X	X	X	X	X	X	X	S	X	
Serum Pregnancy Test 	S								S			

Period	Screening	Treatment									Follow-up	
Visit Name	Visit 1 Screening	Visit 2 (home visit)	Visit 3 (home visit)	Visit 4 (office visit)	Visit 5 Visit 6 Visit 7 (home visit)	Visit 8 (office visit)	Visit 9 (office visit)	Visit 10 (office visit)	Visit 11/ End of Study – EOS (office visit)	Visit 12 / Safety (remote contact)	Unscheduled	
Day/Week/Month	Day -7	Day 1	Day 29	Day 43	Day 50 Day 57 Day 71	Day 99	Day 209	Day 299	Day 389	Day 419		
Visit Window				+/-3d	+/-3d	+/-3d	+/-3d	+/-3d	+/-3d	+/-3d		
Self-Injection Training				S								
Office administration of study drug				X		X						
Dispense study drug for future home administration				X		X	X	X				
Home administration of study drug					X							
Patient Diary/Drug Accountability				X	X	X	X	X	X			
Adverse Events / Serious Adverse Events	X	X	X	X	X	X	X	X	X	S	X	
Subject disposition	X								X	S		
Vaccine check-in contacts 		S	S									
Remote check-in 					S					S		

X = assessment to be recorded in the clinical database or received electronically from a vendor

S = assessment to be recorded in the source documentation only

 Serum pregnancy should be performed locally for all sites except those unable to use a local lab. Sites unable to perform locally should send sample to the central lab.

 Participants with lab results within the past 6 months prior to screening will not require labs drawn at screening visit. Local labs should be documented in the source. Participants without lab results from the past 6 months prior to screening will require central labs drawn at the screening visit to be entered into the clinical database.

 Sample will be bio-banked for yet to be identified analyses.

 Vaccine check-ins (remote contacts) by site staff to confirm participant has received the COVID-19 vaccine and to collect any AEs/SAEs.

 Remote contact with participants by site staff. The contact should query about receipt any new AEs or SAEs. Method of contact can be via telephone, email or text message depending on the preference of each participant.

**Table 8-3 Assessment schedule for Cohorts 2 and 3 (Pfizer vaccine)**

Period	Screening	Treatment						Follow-up	
Visit Name	Visit 1 Screening	Visit 2	Visit 3	Visit 4	Visit 5	Visit 6	Visit 7/End of Study (EOS)	Visit 8 / Safety	Unscheduled
Day/Week/Month	Day -7	Day 1	Day 22	Day 36	Day 202	Day 292	Day 382	Day 412	
Visit Window				+3d	+/-3d	+/-3d	+/-3d	+/-3d	
Obtain informed consent	X								
Inclusion/exclusion criteria	X								
Demography	X								
Relevant medical history/current medical history	X								
Non-drug therapies and procedures	X	X	X	X	X	X	X	S	X
Prior/Concomitant Medications	X	X	X	X	X	X	X	S	X
MS Relapse	X	X	X	X	X	X	X	S	X
Serum Pregnancy Test 	S						S		

Period	Screening	Treatment						Follow-up	
Visit Name	Visit 1 Screening	Visit 2	Visit 3	Visit 4	Visit 5	Visit 6	Visit 7/End of Study (EOS)	Visit 8 / Safety	Unscheduled
Day/Week/Month	Day -7	Day 1	Day 22	Day 36	Day 202	Day 292	Day 382	Day 412	
Visit Window				+3d	+/-3d	+/-3d	+/-3d	+/-3d	
Hepatitis B virus (HBV) (Cohort 2 only) 	X								
SARS CoV2 qualitative antibody		X	X	X	X	X	X		
Serum Immunoglobulin 	X				X		X		
CD 19+ B cells (Cohort 2 only)	X	X	X	X	X	X	X		
Biobanked serum sample 	X			X					
Biobanked whole blood sample 	X			X					
Vaccine Administration Form		X	X						
IRT Transaction	X	X	X	X	X	X	X		
Drug Accountability		S	S	S	S	S	S		
Adverse Events / Serious Adverse Events	X	X	X	X	X	X	X	S	X
Subject disposition	X						X	S	

X = assessment to be recorded in the clinical database or received electronically from a vendor

S = assessment to be recorded in the source documentation only

 Serum pregnancy should be performed locally for all sites except those unable to use a local lab. Sites unable to perform locally should send sample to the central lab.

 Participants with lab results within the past 6 months prior to screening will not require labs drawn at screening visit. Local labs should be documented in the source. Participants without lab results from the past 6 months prior to screening will require central labs drawn at the screening visit to be entered into the clinical database.

 Sample will be bio-banked for yet to be identified analyses.

 Vaccine check-ins (remote contacts) by site staff to confirm participant has received the COVID-19 vaccine and to collect any AEs/SAEs.

 Remote contact with participants by site staff. The contact should query about receipt any new AEs or SAEs. Method of contact can be via telephone, email or text message depending on the preference of each participant.

**Table 8-4 Assessment schedule for Cohorts 2 and 3 (Moderna vaccine)**

Period	Screening	Treatment						Follow-up	
Visit Name	Visit 1 Screening	Visit 2	Visit 3	Visit 4	Visit 5	Visit 6	Visit 7/End of Study (EOS)	Visit 8 / Safety	Unscheduled
Day/Week/Month	Day -7	Day 1	Day 29	Day 43	Day 209	Day 299	Day 389	Day 419	
Visit Window				+3d	+/-3d	+/-3d	+/-3d	+/-3d	
Non-drug therapies and procedures	X	X	X	X	X	X	X	S	X
Prior/Concomitant Medications	X	X	X	X	X	X	X	S	X
MS Relapse	X	X	X	X	X	X	X	S	X
Serum Pregnancy Test 	S						S		
Hepatitis B virus (HBV) (Cohort 2 only) 	X								
SARS CoV2 qualitative antibody		X	X	X	X	X	X		
Serum Immunoglobulin 	X				X		X		
CD 19+ B cells (Cohort 2 only)	X	X	X	X	X	X	X		
Biobanked serum sample 	X			X					
Biobanked whole blood sample 	X			X					

Period	Screening	Treatment						Follow-up	
Visit Name	Visit 1 Screening	Visit 2	Visit 3	Visit 4	Visit 5	Visit 6	Visit 7/End of Study (EOS)	Visit 8 / Safety	Unscheduled
Day/Week/Month	Day -7	Day 1	Day 29	Day 43	Day 209	Day 299	Day 389	Day 419	
Visit Window				+3d	+/-3d	+/-3d	+/-3d	+/-3d	
Vaccine Administration Form		X	X						
IRT Transaction	X	X	X	X	X	X	X		
Drug Accountability		S	S	S	S	S	S		
Adverse Events / Serious Adverse Events	X	X	X	X	X	X	X	S	X
Subject disposition	X						X	S	
Vaccine check-in contacts 		S	S						
Remote check-in 								S	

X = assessment to be recorded in the clinical database or received electronically from a vendor

S = assessment to be recorded in the source documentation only

 Serum pregnancy should be performed locally for all sites except those unable to use a local lab. Sites unable to perform locally should send sample to the central lab.

 Participants with lab results within the past 6 months prior to screening will not require labs drawn at screening visit. Local labs should be documented in the source. Participants without lab results from the past 6 months prior to screening will require central labs drawn at the screening visit to be entered into the clinical database.

 Sample will be bio-banked for yet to be identified analyses.

 Vaccine check-ins (remote contacts) by site staff to confirm participant has received the COVID-19 vaccine and to collect any AEs/SAEs.

 Remote contact with participants by site staff. The contact should query about receipt any new AEs or SAEs. Method of contact can be via telephone, email or text message depending on the preference of each participant.

**Table 8-5 Assessment schedule for Cohorts 4, 5 and 6 (Pfizer vaccine)**

Period	Screening	Treatment				Follow-up	Unscheduled
		Visit 1 Screening	Visit 2	Visit 3	Visit 4		
Visit Name	Visit 1 Screening	Visit 2	Visit 3	Visit 4	Visit 5/End of Study (EOS)	Visit 6 / Safety	Unscheduled
Day/Week/Month	Day -7	Day 1	Day 202	Day 292	Day 382	Day 412	
Visit Window			+/-3d	+/-3d	+/-3d	+/-3d	
Obtain informed consent	X						
Inclusion/exclusion criteria	X						
Demography	X						
Relevant medical history/current medical history	X						
Non-drug therapies and procedures	X	X	X	X	X	S	X
Prior/Concomitant Medications	X	X	X	X	X	S	X
MS Relapse	X	X	X	X	X	S	X
Local Serum Pregnancy Test 	S				S		
Hepatitis B virus (HBV) (Cohort 4 and 6 only)	X						
SARS CoV2 qualitative antibody		X	X	X	X		
SARS-CoV-2 nucleocapsid antibody		X					

Period	Screening	Treatment				Follow-up	
Visit Name	Visit 1 Screening	Visit 2	Visit 3	Visit 4	Visit 5/End of Study (EOS)	Visit 6 / Safety	Unscheduled
Day/Week/Month	Day -7	Day 1	Day 202	Day 292	Day 382	Day 412	
Visit Window			+/-3d	+/-3d	+/-3d	+/-3d	
Serum Immunoglobulin 	X		X		X		
CD 19+ B cells (Cohort 4 and 6 only)	X	X	X	X	X		
Biobanked serum sample 	X						
Biobanked whole blood sample 	X						
Vaccine Administration Form	X						
IRT Transaction	X	X	X	X	X		
Drug Accountability		S	S	S	S		
Adverse Events / Serious Adverse Events	X	X	X	X	X	S	X
Subject disposition	X				X	S	
Remote check-in 						S	

X = assessment to be recorded in the clinical database or received electronically from a vendor

S = assessment to be recorded in the source documentation only

 Serum pregnancy should be performed locally for all sites except those unable to use a local lab. Sites unable to perform locally should send sample to the central lab.

 Participants with lab results within the past 6 months prior to screening will not require labs drawn at screening visit. Local labs should be documented in the source. Participants without lab results from the past 6 months prior to screening will require central labs drawn at the screening visit to be entered into the clinical database.

 Sample will be bio-banked for yet to be identified analyses.

 Remote contact with participants by site staff. The contact should query about receipt any new AEs or SAEs. Method of contact can be via telephone, email or text message depending on the preference of each participant.

**Table 8-6 Assessment schedule for Cohorts 4, 5 and 6 (Moderna vaccine)**

Period	Screening	Treatment				Follow-up	
Visit Name	Visit 1 Screening	Visit 2	Visit 3	Visit 4	Visit 5/End of Study (EOS)	Visit 6 / Safety	Unscheduled
Day/Week/Month	Day -7	Day 1	Day 209	Day 299	Day 389	Day 419	
Visit Window			+/-3d	+/-3d	+/-3d	+/-3d	
Obtain informed consent	X						
Inclusion/exclusion criteria	X						
Demography	X						
Relevant medical history/current medical history	X						
Non-drug therapies and procedures	X	X	X	X	X	S	X
Prior/Concomitant Medications	X	X	X	X	X	S	X
MS Relapse	X	X	X	X	X	S	X
Local Serum Pregnancy Test 	S				S		
Hepatitis B virus (HBV) (Cohort 4 and 6 only)	X						
SARS CoV2 qualitative antibody		X	X	X	X		
SARS-CoV-2 nucleocapsid antibody		X					

Period	Screening	Treatment				Follow-up	
Visit Name	Visit 1 Screening	Visit 2	Visit 3	Visit 4	Visit 5/End of Study (EOS)	Visit 6 / Safety	Unscheduled
Day/Week/Month	Day -7	Day 1	Day 209	Day 299	Day 389	Day 419	
Visit Window			+/-3d	+/-3d	+/-3d	+/-3d	
Serum Immunoglobulin 	X		X		X		
CD 19+ B cells (Cohort 4 and 6 only)	X	X	X	X	X		
Biobanked serum sample 	X						
Biobanked whole blood sample 	X						
Vaccine Administration Form	X						
IRT Transaction	X	X	X	X	X		
Drug Accountability		S	S	S	S		
Adverse Events / Serious Adverse Events	X	X	X	X	X	S	X
Subject disposition	X				X	S	
Remote check-in 						S	

X = assessment to be recorded in the clinical database or received electronically from a vendor

S = assessment to be recorded in the source documentation only

 Serum pregnancy should be performed locally for all sites except those unable to use a local lab. Sites unable to perform locally should send sample to the central lab.

 Participants with lab results within the past 6 months prior to screening will not require labs drawn at screening visit. Local labs should be documented in the source. Participants without lab results from the past 6 months prior to screening will require central labs drawn at the screening visit to be entered into the clinical database.

 Sample will be bio-banked for yet to be identified analyses.

 Remote contact with participants by site staff. The contact should query about receipt any new AEs or SAEs. Method of contact can be via telephone, email or text message depending on the preference of each participant.

## **8.1 Screening**

Rescreening is not permitted.

### **8.1.1 Eligibility screening**

#### **8.1.1.1 Hepatitis screen**

Hepatitis B virus (HBV) will be performed at Visit 1/Screening for participants in Cohort 1, 2, 4 and 6 that do not have test results in their medical history within 6 months prior to the Screening Visit/Day -7.

#### **8.1.1.2 Serum Immunoglobulins**

Total serum immunoglobulins will be performed at Visit 1/Screening for all participants that do not have test results in their medical history within 6 months prior to the Screening Visit/Day -7.

### **8.1.2 Information to be collected on screening failures**

Participants who sign an informed consent form and subsequently found to be ineligible prior to enrollment will be considered a screen failure. The reason for screen failure should be recorded on the appropriate Case Report Form. The demographic information, informed consent, cohort, Protocol Amendment log and Inclusion/Exclusion pages must also be completed for screen failure participants. No other data will be entered into the clinical database for participants who are screen failures, unless the participant experienced a serious adverse event during the screening phase (see SAE section for reporting details). If the participant fails to be enrolled, the IRT must be notified within 2 days of the screen fail that the participant was not enrolled.

Participants who are enrolled and fail to start treatment, e.g. participants enrolled in error, will be considered an early terminator. The reason for early termination should be recorded on the appropriate Case Report Form.

## **8.2 Participant demographics/other baseline characteristics**

Participant demographic data and baseline characteristics to be collected on the participants include: age, sex, race and ethnicity. Relevant medical history/current medical condition data includes data collected up to the point in which informed consent is signed. Where possible, diagnoses, and not symptoms will be recorded. Investigators will have the discretion to record abnormal test findings on the CRF capturing medical history whenever in their judgment, the test abnormality occurred prior to the informed consent signature.

## **8.3 Efficacy**

Not applicable.

## **8.4 Safety**

For details on AE collection and reporting, refer to AE section.

#### **8.4.1     Laboratory evaluations**

Clinically significant abnormalities must be recorded as either medical history/current medical conditions or adverse events as appropriate.

A central laboratory will be used for analysis of all specimen collected listed below with the exception of the serum pregnancy test. Details on the collection, shipment of samples and reporting of results by the central laboratory are provided to investigators in the central laboratory manual.

In the case where a laboratory range is not specified by the protocol, but a value is outside the reference range for the laboratory at screening and/or initial baseline, a decision regarding whether the result is of clinical significance or not shall be made by the Investigator (in consultation with the sponsor) and shall be based, in part, upon the nature and degree of the observed abnormality. The assessment may be repeated once prior to enrollment/Visit 2.

In all cases, the Investigator must document in the source documents, the clinical considerations (i.e., result was/was not clinically significant and/or medically relevant) in allowing or disallowing the participant to continue in the study.

Follow instructions outlined in the laboratory manual regarding sample collection, numbering, processing, and shipment.

#### **8.4.2     Pregnancy and assessments of fertility**

All pre-menopausal women who are not surgically sterile will have pregnancy testing. A serum pregnancy test will be performed for all women of child-bearing potential at Screening Visit/Day -7 and the End of Study Visit. Serum pregnancy should be performed locally for all sites except those unable to use a local lab. Sites unable to perform locally should send sample to the central lab.

Additional pregnancy testing might be performed if requested by local requirements.

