#### 1. Screening Period:

Participants will enter a Screening Period of up to 7 days to assess eligibility requirements. Participants in Cohort 1, 2, 4 and 6 without Hepatitis B virus (HBV) and total serum immunoglobulin results within the past 6 months prior to screening will require central labs drawn. Participants with Hepatitis B virus (HBV) and total serum immunoglobulin results within the specified inclusion range the past 6 months prior to screening will not require the labs to be drawn.

Participants in Cohort 3 and 5 without total serum immunoglobulin results within the past 6 months prior to screening will require central labs drawn. Participants with total serum immunoglobulin results within the specified inclusion range the past 6 months prior to screening will not require the labs to be drawn.

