## **4.5 Risks and benefits**

There is no benefit expected for participants in this study. Their participation will help contribute to a better understanding of the immune response that occurs when participants receiving ofatumumab are given a COVID-19 mRNA vaccine.

The risk to participants in this trial may be minimized by compliance with the eligibility criteria and study procedures, close clinical monitoring, avoidance of prohibited treatments and adherence to investigator guidance regarding specific safety areas. For further details about ofatumumab, please refer to the Investigator's Brochure (IB) and USPI.

Ofatumumab is approved for the treatment of RMS in several countries. Over 1500 RMS participants have been exposed to ofatumumab across phase 2 and phase 3 studies. In the

pivotal Phase 3 studies COMB157G2301 and COMB157G2302, treatment with ofatumumab significantly lowered the annualized relapse rate (ARR; primary endpoint) compared to the active comparator teriflunomide by >50%. Ofatumumab also significantly reduced the risk of disability progression by >30% and showed significant suppression of both gadolinium (Gd)-enhancing T1 lesions (>90%) and new/enlarging T2 lesions (>80%) on brain MRI compared to teriflunomide.

The data from the ofatumumab program in MS indicates ofatumumab to have an acceptable safety profile and to be well tolerated at the recommended subcutaneous dose of 20 mg. Adverse reactions in the MS population included upper respiratory tract infections, decreased immunoglobulin M, injection site reaction, and injection related reactions. For further details about ofatumumab, please refer to the IB and USPI.

Overall, the balance of benefit and risk supports the proposed clinical study to evaluate the potential of ofatumumab s.c as an effective and safe therapy to address the unmet medical need of participants with RMS.

Women of child-bearing potential must be informed that taking the study treatment may involve unknown risks to the fetus if pregnancy were to occur during the study, and agree that in order to participate in the study they must adhere to the contraception requirements outlined in the exclusion criteria. If there is any question that the participant will not reliably comply, they should not be entered or continue in the study.

Novartis will supply participants in Cohort 1 with ofatumumab treatment as per the assessment schedules in [Table 8-1](#) and [Table 8-2](#).

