## 5.2 Exclusion criteria

Participants meeting any of the following criteria are not eligible for inclusion in this study:

1. Already has received the J&J vaccine.
2. Has a contraindication to receiving an mRNA COVID-19 vaccine
3. Has an immediate allergic reaction to past vaccine or injection
4. Any safety finding including low immunoglobulin IgG and/or low immunoglobulin IgM levels requiring an ofatumumab treatment interruption within the 12 weeks immediately prior to vaccination as determined by the HCP
5. Any major episode of infection requiring hospitalization or treatment with intravenous antibiotics within 4 weeks prior to the first vaccination visit or oral antibiotics within two weeks prior to the first vaccination visit
6. Prior treatment with B-cell targeted therapies (e.g., rituximab or ocrelizumab), alemtuzumab, anti-CD4, cladribine, cyclophosphamide, mitoxantrone, azathioprine, mycophenolate mofetil, cyclosporine, methotrexate, total body irradiation, or bone marrow transplantation
7. Prior treatment with S1P agent within 2 months at Screening
8. Prior treatment with natalizumab within 6 months of study enrollment
9. Since commercially prescribed ofatumumab is being used in the study, contraindications as per the USPI will be adhered to which include active infection hepatitis B infection, progressive multifocal leukoencephalopathy and pregnancy.
10. Participation in another interventional clinical trial within 14 days before enrollment.
11. Use of other investigational drugs at the time of enrollment (Screening) or within the prior 30 days, or five elimination half-lives, or until the expected pharmacodynamic effect has returned to baseline, whichever is longer.
12. History of hypersensitivity to any of the study treatments or its excipients or to drugs of similar chemical classes.
13. Have been treated with any of the medications listed below within the time specified:

Medication	Exclusionary if used within the timeframe specified below
Intravenous, oral, intra-articular or intramuscular corticosteroids, adrenocorticotropic hormone	30 days prior to Screening

Medication	Exclusionary if used within the timeframe specified below
Immunosuppressive, chemotherapeutic medications (e.g. mitoxantrone, cyclophosphamide, cladribine, S1P modulators)	2 months prior to first study drug administration
Natalizumab	Within 6 months of study enrollment/Visit 2

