#### **Participants in Cohort 1**

Ofatumumab will be provided in an auto injector for subcutaneous administration containing 20 mg ofatumumab (20 mg/0.4 ml). Treatment should be administered after study assessments have been completed for the visit.

Cohort 1 should receive their first loading dose of ofatumumab at Visit 4 which should be held 2 weeks after receiving their 2nd COVID-19 vaccine dose.

Site staff should remove the study treatment from the refrigerator and allow the auto injector pen to reach room temperature in their unopened box (approximately 15-30 minutes) before self-injection by the participant. Used syringes should be disposed of immediately after use in a sharps container.

A different body site (front of thighs, lower abdomen) should be chosen each time a dose is administered to reduce the risk of an injection-site reaction; investigator/qualified site staff/caregiver can also inject the study treatment in the outer upper arms. Each new injection should be given at least one inch from the previously used site. If administration is in the abdomen, the 2-inch area around navel should be avoided. Study treatment should also not be injected into areas where the skin is tender, bruised, red, or hard, or where the participant has scars or stretch mark

As participants must self-administer ofatumumab, site personnel will provide training on the correct procedure for injection technique of the ofatumumab subcutaneous injections to enable the participant and/or a caregiver to administer from home in-between scheduled office visits. Documentation of the participant or caregiver understanding the correct administration procedure must be documented in the source document. Participants will be instructed to contact the investigator/site staff prior to self-administration at home if they are experiencing any AE/SAEs or have any concerns.

Site personnel will make remote contact with participants in Cohort 1 on/around the time of the 2nd loading dose to query about any new or worsening symptoms warranting an unscheduled visit, compliance with study treatment, injection reactions, and compliance with contraception requirements when applicable.

Additional remote contacts should be conducted on/around the time participants are due to administer treatment at home. The method of contact with each participant can be the personal

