**Table 6-3 Dose and treatment schedule**

	Investigational Drug	Frequency and/or Regimen
Cohort 1	OMB157 20mg/0.4mL	Day 36, 43, 50, 64 and monthly thereafter for participants that receive the Pfizer vaccine. Day 43, 50, 57, 71 and monthly thereafter for participants that receive the Moderna vaccine.
Cohort 2	OMB157 20mg/0.4mL	Monthly as prescribed
Cohort 3	Interferon or glatiramer acetate	As prescribed
Cohort 4	OMB157 20mg/0.4mL	As prescribed
Cohort 5	Interferon or glatiramer acetate	As prescribed
Cohort 6	OMB157 20mg/0.4mL	As prescribed

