### **Special guidance regarding the scheduling of visits for Cohorts 1, 2 and 3**

- The study site will need to perform Vaccine Status Check-ins (make remote contact with participant) to confirm when the 1st and 2nd COVID-19 vaccinations are scheduled in order to schedule Visit 4.
- The date of the 2nd COVID-19 vaccine dose will determine the date of Visit 4 and all other remaining study visits.
- Visits 2 and 3 should always occur prior to administration of the mRNA vaccine.
- The Visit 4 lab samples should be collected 14 days after a participant has received their 2nd COVID-19 vaccine dose.

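### Cohort 1 starts ofatumumab at Visit 4 with no pregnancy test scheduled since Screening, five to seven weeks earlier

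*Protocol*

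**What the plan says.** Section 8.4.2 of the protocol sets the testing schedule for every cohort: "A serum pregnancy test will be performed for all women of child-bearing potential at Screening Visit/Day -7 and the End of Study Visit". It allows further tests only where local requirements ask for them, and Section 8.5 rules out additional tests. In Table 8-2 (Cohort 1, Moderna) the row "Serum Pregnancy Test" is marked at Visit 1 and at Visit 11/End of Study and is blank at Visit 4. The matching row of Table 8-1 (Cohort 1, Pfizer) is not in the text available for this review, so for Pfizer the point rests on Section 8.4.2.

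On timing, Section 3 says "Participants will enter a Screening Period of up to 7 days to assess eligibility requirements". Section 6.3.2 says "Cohort 1 should receive their first loading dose of ofatumumab at Visit 4", two weeks after the second vaccine dose. Table 6-3 gives the ofatumumab days as "Day 36, 43, 50, 64 and monthly thereafter for participants that receive the Pfizer vaccine", with Day 43 as the first dose for Moderna. Section 8 adds, of the second injection, that the "vaccine dose will determine the date of Visit 4 and all other remaining study visits".

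On pregnancy, exclusion criterion 9 in Section 5.2 says that "contraindications as per the USPI will be adhered to which include active infection hepatitis B infection, progressive multifocal leukoencephalopathy and pregnancy". Section 4.5 tells women that the risk to a fetus is unknown and that, to take part, "they must adhere to the contraception requirements outlined in the exclusion criteria".

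**The concern.** In Cohorts 2, 4 and 6 participants are already taking commercially prescribed ofatumumab, and in Cohorts 3 and 5 they stay on interferon or glatiramer acetate. Only in Cohort 1 does the trial supply the drug and decide when it starts. That start is deliberately held back until a full vaccine course has been given, but the pregnancy test is not moved with it. Table 8-2 also places the inclusion and exclusion check at Screening only.

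A woman who conceives after Screening could thus receive her first loading dose with no scheduled test to reveal the pregnancy. What is at stake is avoidable fetal exposure to a drug that the trial itself starts, under a protocol that says it will respect the pregnancy contraindication. No endpoint, estimand or analysis is involved.

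**Working it through.** **Inputs**
- Second vaccine dose: Day 22 (Pfizer) or Day 29 (Moderna), from Tables 8-1 and 8-2.
- First ofatumumab dose: 14 days later, at Visit 4 (Section 6.3.2, Table 6-3).
- Screening test: from Day -7 up to about Day 1 (Sections 3 and 8.4.2).
- Visit 4 window in Cohort 1: plus or minus 3 days (Tables 8-1 and 8-2).
- Cohort 1 size: 22 (Section 5).

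**The plan's own dosing days**
- Pfizer: 22 + 14 = Day 36.
- Moderna: 29 + 14 = Day 43.

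Both agree with Table 6-3.

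**Interval from test to first dose**

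The interval is the Visit 4 day minus the test day, counted without a Day 0. If a Day 0 is counted, the intervals from Day -7 become one day longer.

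| | Test at Day 1 | Test at Day -7 | With the 3-day window |
|---|---|---|---|
| Pfizer | 36 - 1 = 35 days (5 weeks) | 36 + 7 - 1 = 42 days (6 weeks) | 35 - 3 = 32 to 42 + 3 = 45 days |
| Moderna | 43 - 1 = 42 days (6 weeks) | 43 + 7 - 1 = 49 days (7 weeks) | 42 - 3 = 39 to 49 + 3 = 52 days |

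These are nominal figures. Visit 4 follows the actual date of the second vaccine dose, so a delayed vaccination lengthens the interval day for day.

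**Expected conceptions in the interval**

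Expected number = women at risk × (interval / 365) × annual contraceptive failure rate.

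The documents do not give the number of women of child-bearing potential, so all 22 are counted as an upper limit. Section 5.2 cites a failure rate below 1% for hormonal methods and also accepts condoms and occlusive caps without giving a rate. A range of 1% to 10% is assumed.

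- Low end: 22 × 35/365 × 0.01 = 0.021
- Longest nominal interval at 1%: 22 × 49/365 × 0.01 = 0.030
- High end: 22 × 49/365 × 0.10 = 0.295

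If only 11 of the 22 were at risk, the range would halve to about 0.01 to 0.15.

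**What happens between Screening and the first dose**

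Adverse events and concomitant medications are recorded at Visits 2, 3 and 4. Vaccine check-ins confirm vaccination and collect adverse events. The remote contact that asks about contraception takes place around the second loading dose, which is after first exposure. None of these steps establishes pregnancy status before the first injection.

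**The case against.** The strongest reply is that the protocol has more protection than the testing schedule suggests.

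- Section 9.1.1 makes pregnancy a mandatory reason to stop study treatment. Section 10.1.4 repeats that treatment should stop and requires every pregnancy after consent to be reported within 24 hours.
- Section 6.3.2 places dosing after the visit's assessments, so the Visit 4 adverse-event and medication review comes before the injection.
- Section 4.5 bars anyone whose contraceptive compliance is in doubt from entering or continuing.
- Contraception arguably covers the interval. Pill users must have been stable for three months before study treatment. The Glossary and Table 6-1 can also be read as making the vaccine a study treatment, so that the requirement would run from the first vaccination.

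These safeguards narrow the gap to an unrecognised pregnancy, and that much stands. They do not close it, because each acts on a pregnancy already known or on contraceptive use, and neither shows status on the day of dosing.

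The objection to the size also has force. The range of 0.02 to 0.3 counts conceptions, not exposures that a test would prevent. Some women would recognise the pregnancy themselves, and a Visit 4 test would miss very recent conceptions. The high end combines several unfavourable assumptions: every participant a woman at risk, all on Moderna, all tested at Day -7, and a 10% rate that the documents do not give. At the documented rate of below 1% the figure is about 0.02 to 0.03 at most over the nominal intervals.

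Finally, the protocol sets no maximum age for the test and promises no test before dosing. No stated rule is broken, and this is a design choice open to improvement.

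**Conclusion.** The concern holds. For Moderna, Section 8.4.2 and Table 8-2 agree that no test is scheduled at Visit 4; for Pfizer, Section 8.4.2 alone supports it. The last scheduled result is five to six weeks old (Pfizer) or six to seven weeks old (Moderna) at the first dose, before any delay in vaccination.

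The probability is low, and the numerical range rests on assumed failure rates and on an unknown number of women at risk. The case does not depend on that range. The protocol names pregnancy as a contraindication, the trial controls when the drug starts, and the check is cheap. The change is worth making on safety grounds and has no bearing on the trial's statistical conclusions.

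**What to change.** In Section 8.4.2 and Tables 8-1 and 8-2, add a pregnancy test at Visit 4 for Cohort 1 women of child-bearing potential, and require a documented negative result before the first ofatumumab injection. This cuts the age of the last test from 35 to 49 days to zero, or to a few days where the sample is taken in advance.

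The recurring cost is one routine test for at most 22 people, at an office visit where blood is already drawn and where dosing already waits for the assessments. The practical difficulty is turnaround, because sites that send pregnancy samples to the central laboratory would not have a same-day result. They should be allowed a urine test at the visit or a serum sample a few days before it. The change also needs a written amendment with sponsor and IRB approval (Section 14.1) across up to 30 centers. Sample size, endpoints and analyses stay as they are.
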